3.4.2 Follow-up Requirements

The schedule of follow-up visits is based on the date of enrollment. Table 4 outlines the time window that is permitted for each of the study interval visits.

Table 4: Study Interval Time Windows

Visit Type	6*, 12, 18, 24, 30, and 36 months	42** and 48** Months
Window	± 60 days*	± 60 days**

*In order to accommodate many patients with Riata/Riata ST silicone leads who were previously enrolled in the “Riata Lead Evaluation Study” in last 10 months, the window for the 6 month visit will be -60 days to + 120 days.

**For only those eligible QuickSite/Quickflex patients that consent to extended follow-up.

Cinefluoroscopy (AP, LAO 45° or the best possible LAO view, RAO 45° or the best possible RAO view) will be taken to determine the incidence/ mechanical progression of externalized conductors at the 12, 24, and 36 month visits for all patients and at the 48 month visit for only those eligible QuickSite/QuickFlex patients that consent for extended follow-up.

If the Riata, Riata ST, QuickSite (1056T/1058T), QuickFlex (1156T/1158T), or Durata lead develops a significant electrical abnormality suggestive of lead malfunction and x-ray or cinefluoroscopy would be performed as per the site's standard of care. The x-ray or cinefluoroscopy should be submitted to SJM.

All patients will be required to attend the in-clinic follow-up visits at 6, 12, 18, 24, 30, and 36 months. Only those eligible QuickSite/QuickFlex patients that consent for extended follow-up will be required to attend the 42 month in-clinic follow-up visit. Data to be captured includes the following:

- RV lead capture threshold, lead pacing impedance and signal amplitude (only required if RV lead model and implant date is listed in Table 1) *
- LV lead capture threshold, lead pacing impedance in a bipolar configuration (only required if LV lead model and implant date is listed in Table 1)
- High Voltage Lead impedance (HVLI) testing – mandatory for Current/ Promote or later ICD and CRT-D, optional for devices before Current/Promote ICD and CRT-D, and not applicable to CRT-P

*** Note:** If patient is pacer dependent or R-wave is not available then RV signal amplitude is not required.

Upon completion of the follow-up above visits, complete the applicable CRFs using the EDC system and submit the supportive data listed below to St. Jude Medical.

- Follow-up CRF
- Product Out of service (if applicable)
- Electronic device session records
- Cinefluoroscopy (AP, LAO 45° or best possible LAO view, RAO 45° or best possible RAO view)

- System Revision (if applicable)

If an adverse event, hospitalization, death, or deviation occurs during the course of study testing and data collection, as applicable, also fill out and submit the following:

- Adverse Event CRF
- Hospitalization CRF
- Deviation CRF
- Death CRF
- Withdrawal CRF
- Supporting documentation of adverse events, deviation(s) from the protocol, and/or death

3.4.3 System Revision

All pulse generator and lead related system revisions should be reported. If a patient's existing Riata, Riata ST, QuickSite (1056T/1058T), QuickFlex (1156T/1158T), or Durata lead is extracted or capped, and no other of the above mentioned leads are still implanted then the patient will be followed for 30 days and withdrawn from the study. It is recommended to provide fluoroscopy data, RV (if applicable) and LV (if applicable) capture threshold, pacing impedance and signal amplitude measurements, and session records at system revision.

Upon completion of system revision, complete the following case report forms using the EDC system and submit the supportive data listed below:

- System Revision
- Product Out of service (if applicable)
- Device session records
- Fluoroscopy/ CXR images (if applicable)
- Adverse Event CRF
- Withdrawal CRF (if applicable)
- Supporting documentation of adverse events, deviation(s) from the protocol, and/or death

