1.0 Introduction

Lead durability and integrity depend on several factors, such as lead design, lead material, and mechanical stress. More than half of all lead complications are insulation defects, most frequently due to subclavian crush syndrome, abrasion of the lead by direct contact to the pulse generator (i.e. pacemaker, ICD, or CRT-D), or abrasion of the lead against adjacent leads. Often these present clinically with evidence of impedance changes or inappropriate ventricular sensing and defibrillation¹.

St. Jude Medical Riata® and Riata® ST family of leads are high voltage implantable cardioverter defibrillator (ICD) endocardial leads with Silicone insulation. QuickSite® and QuickFlex® left ventricular leads also utilize silicone rubber for insulation. Silicone rubber, while representing the industry's most commonly used defibrillation lead insulation material over the past 20 years, has been observed to be vulnerable to abrasion^{2,3,4}. Abrasion of silicone defibrillation leads is acknowledged within the clinical community as a well known clinical risk and is well documented in the literature as the number one cause of lead failure across the industry with reported failure rates ranging from 3 to 10 %^{5,6,7}.

A more recently reported manifestation of Riata lead insulation and QuickSite/QuickFlex lead abrasion involves conductors that are outside the lead body as detected by x-ray, fluoroscopy, or post-explant physical examination. This phenomenon, known as inside-out abrasion with externalized conductors, occurs when internal abrasion processes produce an outer insulation breach significant enough to allow the conductor to separate from the lead body in isolated regions. Such a separation does not guarantee an electrical abnormality because the conductors themselves are insulated with a robust layer of ethylenetetrafluoroethylene (ETFE) polymer.

The prevalence of externalized conductors proximal to the RV coil in Riata/Riata ST leads has been reported to vary from 0.5% to 33.3% depending on the lead model⁸⁻¹¹. Some of these cases of externalized conductors have been accompanied with inappropriate shocks, oversensing, increased pacing impedance/ threshold and lead noise. It remains unclear whether externalized conductors caused these electrical problems, as approximately 85% of the returned leads with externalized conductors do not have their ETFE insulation compromised and therefore should not be the cause of any reported electrical problem.

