3.0 Clinical Protocol

3.1 Study Design and Scope

This study is a prospective, non-randomized, multi-center, international post market study that will determine the prevalence and incidence of externalized conductors and other visual lead anomalies (as evidenced by imaging) and the risk of progression to electrical dysfunction in a large series of ICD/ CRT-D/CRT-P devices containing one or more of the following SJM leads: Riata leads, Riata ST silicone leads, Durata leads, QuickSite/QuickFlex CRT leads. A patient that has at least one market released lead implanted in time period indicated in Table 1 is eligible for enrollment in the study. Each lead group will be considered separately for independent analysis.

Table 1: Leads Eligible for Enrollment

Lead Group	Model Numbers	Lead Implant Date
Riata	1560, 1561, 1562, 1570, 1571, 1572, 1580, 1581, 1582, 1590, 1591, 1592	2002-2009
Riata ST Silicone	7000, 7001, 7002, 7010, 7011, 7040, 7041, 7042	2006-2009
QuickSite/QuickFlex	1056T, 1058T, 1156T, 1158T	2006-2010
Durata	7120, 7121, 7122, 7130, 7131, 7120Q, 7121Q, 7122Q, 7170Q, 7171Q, 7172Q	2008-2010

In order to determine the prevalence and incidence of externalized conductors, other visual lead anomalies as well as electrical dysfunction in the population of leads being evaluated, a minimum of 1500 leads listed above will be enrolled at up to 60 sites. This will comprise a minimum of 300 leads in the Riata lead group and a minimum of 200 leads in the Riata ST lead group to make a combined total of at least 500 Riata and Riata ST silicone leads. The study will also include at least 500 leads in the QuickSite/QuickFlex and Durata lead groups. All patients will be followed every six months for three years.

Adequate representation across the different ages of the leads is also needed to understand the lead population being studied. Therefore, the leads from each group of leads will be compromised of subgroups based on the age of lead (at enrollment) being studied. The required minimum enrollment for each subgroup per lead group is indicated in Table 2. Even if the minimum enrollments indicated in Table 2 are met, extra enrollments may be required to ensure a minimum of 500 leads in each lead group.

Expected Attrition in patients with high voltage leads

Withdrawals due to death

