*Expected attrition in each of the lead groups is based on the rationale provided above the table as well as larger attrition expected in older leads.

[figure not shown]
At enrollment, medical history, demographic data and lead measurement data will be collected. Additionally, cinefluoroscopy (AP, LAO 45° or the best possible LAO view, RAO 45° or the best possible RAO view) will be performed to determine the prevalence of lead compromise. A copy of

cinefluoroscopy performed as part of separate screening can be used to determine the prevalence of lead compromise as long as all three views (AP, LAO 45° or the best possible LAO view, RAO 45° or the best possible RAO view) are available. In patients with evidence of externalized conductors or other visual lead anomalies (fracture, subclavian crush, kink, broken filars on a shocking coil and other irregularities) the following chest x-rays or other available imaging studies will be collected (if available): a) earliest imaging study showing evidence of externalized conductors or other visual lead anomaly and b) latest imaging study that does not show any evidence of externalized conductors or other visual lead anomaly

Data will be collected at 6, 12, 18, 24, 30, and 36 months post enrollment and during any unscheduled follow-up visits due to patient symptoms suggestive of or with evidence of lead electrical problems. Additionally, cinefluoroscopy (AP, LAO 45° or the best possible LAO view, RAO 45° or the best possible RAO view) will be performed in all patients to determine the incidence and mechanical progression of externalized conductors at the 12, 24, and 36 month visits.

During any follow-up visits, device data and stored electrograms will be collected. All clinical events such as hospitalizations, emergency room visits, and adverse events will also be collected. All study data, including device data and stored electrograms will be sent to SJM electronically. If any lead being followed in this study develops a significant electrical abnormality suggestive of lead malfunction and x-ray or cinefluoroscopy would be performed as per the site standard of care then copies of x-ray or cinefluoroscopy should be submitted to SJM.

During the course of the study, any explanted leads should be returned to Returned Goods, St Jude Medical, Sylmar, CA, for analysis.

Study Flow Diagram

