11.2 Cinefluoroscopy Adjudication Committee

Cinefluoroscopy Adjudication Committee (CAC) will be comprised of at least three Electrophysiologists or Cardiologists specially trained in using Cinefluoroscopy in this patient population. The role of the CAC is to adjudicate the cinefluoroscopy videos/images to determine the presence of lead compromise in the SJM Cardiac Lead Assessment study patient population. Committee members will be reviewing the cinefluoroscopy videos/images for the enrollment, 12, 24, and 36 month follow-up visits and any additional cinefluoroscopy videos/images received during the course of the study. Data will be sent either electronically or on a disk to the committee members. Once the adjudication is complete, a cinefluoroscopy adjudication form will be collected per patient per study visit. If the presence of externalized conductors is deemed to be ‘indeterminate’ then the cinefluoroscopy will be further reviewed by two other CAC members. Sample pictures/fluoros/x-rays and other examples of “other visual lead anomalies” will be provided to the adjudication committee to aid the committee members in identifying these “other visual lead anomalies” on the cinefluoroscopy videos/images received from the site.

Only the adjudicated imaging data will be included in the post market surveillance reports. Percentage of leads with compromise, evidenced by imaging, will be presented in the report. The type, extent and location of

lead compromise, as described in Appendix A, will also be included. As detailed in Appendix A, each region of the HV as well as CRT leads is divided into different regions. Both the proximal as well as distal ends of externalization will be recorded by the cinefluoroscopy adjudication committee. The distribution of externalization (both absolute number and percentage) by each region of the lead will be presented for both proximal and distal ends of externalization. The distribution of “other visual lead anomalies” (both absolute number and percentage) by each region of the lead and each individual subcategory of “other visual lead anomalies” will be presented. The frequency (both absolute number as well as percentage) of individual subcategories will be reported for “other visual lead anomalies”.

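### Leads that externalize after their last cine and are removed with no image submitted enter incidence without an event: a small effect on overall incidence, a larger concern for the link to electrical dysfunction

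*Combined protocol and SAP*

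**What the plan says.** - **Scheduled imaging.** After the enrollment cine, section 3.4.2 requires cinefluoroscopy "at the 12, 24, and 36 month visits for all patients", with a window of 60 days either side. Consenting QuickSite/QuickFlex patients have one more at 48 months.
- **Imaging at removal.** Section 3.4.3 states "It is recommended to provide fluoroscopy data". Images are on its submission list only where applicable.
- **Imaging when an electrical abnormality appears.** Section 3.1 conditions submission on whether "x-ray or cinefluoroscopy would be performed as per the site standard of care". Section 3.4.2 is to the same effect.
- **What is reported.** Section 11.2 states "Only the adjudicated imaging data will be included in the post market surveillance reports". The same section has the cine committee (CAC) review "any additional cinefluoroscopy videos/images received during the course of the study", so an image that a site does send can make a lead a case.
- **Returned leads.** The introduction describes externalization as "conductors that are outside the lead body as detected by x-ray, fluoroscopy, or post-explant physical examination". Section 3.1 asks for explanted leads to be returned. What is found on them goes to primary outcome 3.2.1.7, whose denominator is returned leads only. Nothing carries it into 3.2.1.5 or 3.2.2.1.
- **Censoring.** Section 3.2.2.1 censors patients without observed externalization at 3 years and has no rule for removed leads.
- **Electrical dysfunction.** Under section 2.0 it exists only in leads that were capped, extracted or electrically abandoned. Under section 11.3 the electrical committee reviews leads taken out of service.

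**The concern.** Removal ends the imaging history of a lead, and nothing in the plan requires a last image at that moment. If the lead externalized since its previous cine, the event is not recorded unless the site happened to send an image. Read literally, the 3-year censoring rule then carries the lead as event-free to 3 years. If it is instead censored at removal, the censoring is informative whenever removal is related to externalization.

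More is at stake in the progression question, which section 1.0 names as something the study will inform physicians about. A lead that externalizes and fails between two cines, with no image sent, is affected twice:
- In 3.2.2.10, endpoint 1, it counts as dysfunction without externalization.
- It never enters 3.2.2.4, where time zero is the detection of externalization.

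Both errors make externalization look less connected to electrical failure than it is.

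**Working it through.** **Plan's own figure.** Section 3.1 gives Riata/Riata ST attrition over 3 years as approximately 43%. Recomputed: 1 − (1 − 0.255)(1 − 0.15)(1 − 0.10) = 0.430. It reproduces. The 10% factor, for leads explanted even with normal function, is the only figure in the document that quantifies lead removal.

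**Leads concerned.** Table 2 targets are 195 + 185 + 180 = 560 Riata and 185 + 180 = 365 Riata ST, 925 in all. Ten percent is 56 and about 37 leads, before any removal for electrical dysfunction.

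**Approximate share lost.** The 10% corresponds to a removal hazard of −ln(0.90)/3 = 0.0351 per year. With annual cines, a new externalization waits about 0.5 year to be seen. If externalized leads are removed k times as often as intact ones, the share removed before being seen is about 0.0351 × k × 0.5: 1.8% for k = 1, 5.3% for k = 3 and 8.8% for k = 5. The externalization rate h cancels out.

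**Fuller model.** States are intact; externalized but unseen; then seen at the next annual cine, removed, or lost. Hazards are constant: removal as above, and death 25.5% and other attrition 15% over 3 years. No image is submitted for any removed lead. The document gives neither h nor k; the assumed ranges are h = 1% to 10% per year and k = 1 to 10.

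For N = 925 and h = 5% per year (about 99 true new cases):

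| k | Cases missed through removal | Share of true cases | Observed rate per 100 lead-years | Rate if those cases were seen |
|---|---|---|---|---|
| 1 | 1.7 | 1.7% | 4.43 | 4.52 |
| 3 | 5.0 | 5.0% | 4.28 | 4.53 |
| 5 | 8.1 | 8.2% | 4.14 | 4.54 |
| 10 | 15.4 | 15.5% | 3.81 | 4.56 |

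The shares hardly move with h. The counts missed for k = 1 to 10 run from 0.4 to 3.2 at h = 1% and from 3.2 to 29.0 at h = 10%. At h = 5% and k = 1, death and other withdrawal lose a further 7.4 cases, which imaging at revision would not recover.

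**Censoring.** With the 10% removal alone, mean follow-up is 3 × 0.10/−ln(0.90) = 2.85 years, against the 3 years that the literal rule credits. With the full 43% attrition it is 3 × 0.43/−ln(0.57) = 2.29 years.

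**Progression analyses.** Let p be the true proportion externalized among dysfunction leads, q the share of those that externalized after the last cine, and u the share of that group with no image submitted. Endpoint 1 of 3.2.2.10 then observes p(1 − qu) in the dysfunction group. Functioning leads still in follow-up go on to their next cine, so this loss falls on one side of the comparison. The document gives none of p, q and u, so no size can be stated; only u can be reduced by the protocol.

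**The case against.** The strongest reply has four parts.

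1. **Returned-lead findings are used.** A reader might infer that they are discarded. They are not: 3.2.1.7 is a primary outcome and its list includes breach of the outer insulation. The sentence in section 11.2 separates adjudicated from unadjudicated images and cannot bar bench data that 3.2.1.7 needs. Section 3.2.1.5 names no way of ascertaining a case, so the exclusion there is inferred from the imaging-based scope in section 3.1 and from section 11.2. Section 6.0 also asks for an adverse event form when externalization appears later, though nothing routes that form into 3.2.1.5. This stands; what remains is that bench findings are reported apart from incidence.
2. **Not every removed lead is affected.** Submitted images are adjudicated, so only leads removed without one are concerned. This stands.
3. **Informativeness is not documented.** It is tempting to say that removed leads are those most likely to have just externalized. No figure here supports that. The 10% refers to recalled leads explanted with normal function, and section 1.0 reports intact conductor insulation in about 85% of returned externalized leads. Externalization that prompted removal because a cine showed it is already a case. This also stands, and k is purely an assumption.
4. **Bench findings bring their own bias.** Only removed and returned leads have that detection route. Adding them to 3.2.2.10 would favour an association, as would damage from the extraction itself. This stands and limits the fix.

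None of these supplies an image for a lead removed between cines when the site sends none.

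**Conclusion.** The gap is real but conditional on no image being submitted, and it should be closed. For overall incidence it is small: about 2% of new cases if removal is unrelated to externalization, and about 5% to 8% at assumed removal ratios of 3 to 5. For a given removal rate and ratio these are upper bounds, because submitted images are adjudicated. Two things could raise them: the 10% excludes removals for electrical dysfunction, and the visit windows allow up to 12 months plus 120 days between two follow-up cines. The figures apply to Riata and Riata ST; the document has no removal rate for the other groups. A reader might conclude that the incidence results are seriously understated, and the calculation does not support that.

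The stronger reason to act is 3.2.2.4 and 3.2.2.10. Every dysfunction case is a lead whose imaging is ending, the final image is optional, and a missed externalization biases toward no link. The direction follows from the definitions; the size cannot be derived from the document.

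**What to change.** 1. **Section 3.4.3.** Replace the recommendation with a requirement to store a set of the protocol views before the study lead is disconnected or moved, whenever the revision is already done under fluoroscopy, and to send it to the CAC. Cost: a short additional recording with a little extra radiation. This is the only step that covers capped leads, which are not returned.
2. **Sections 3.2.1.5 and 3.2.2.1.** Keep the imaging-based analyses as primary. Add a sensitivity analysis that counts externalization found on returned-lead examination as interval-censored between the last negative cine and removal. Count only a conductor outside the lead body, not any breach of the outer insulation, and flag cases first seen after extraction. State where removed leads with no finding are censored. Cost: one analysis on leads already being examined, and a bench record that separates the two findings.
3. **Section 3.2.2.10, endpoint 1.** Show returned-lead cases only as a separate, labelled sensitivity result. State that functioning leads lack this detection route and that capped leads are not covered. Cost: one extra table row and a sentence.

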3.4.4 Unscheduled Follow-up

Unscheduled follow-up visit data will be captured if patients present in the clinic with any symptoms suggestive of or with evidence of lead related electrical problems for non protocol specified visits. It is recommended to do all the applicable RV and

LV (if applicable) lead measurements at that time. A follow-up CRF must be submitted for these unscheduled visits.

3.4.5 Extended Follow-up (Eligible QuickSite/QuickFlex patients only)

The purpose of extending follow-up for eligible patients with QuickSite/QuickFlex leads is to address challenges with fulfilling the minimum number of leads to enroll for the QuickSite/QuickFlex lead group/subgroups as shown in Table 2.

The extended follow-up will help address this issue since the data from patients with extended follow-up will contribute to 2 separate sub-group cohorts for the primary and secondary outcome measure analyses.

For example, a patient who was enrolled with a QuickSite/QuickFlex lead that was implanted for 5 years at the time of enrollment will contribute to the ≥ 5 to <6 year age of lead subgroup cohort (data from lead 5, 6, 7, and 8 years implanted). After this patient provides consent and completes the additional year of follow-up, this patient will also contribute to the ≥ 6 year age of lead subgroup cohort (data from lead 6, 7, 8, and 9 years implanted) as shown in Table 5 below.

Table 5: Extended Follow-Up Example

QS/QF Subgroup cohort Age of Lead @ Enrollment	Primary and Secondary Outcome Measure Data Analyses Timepoints				Extended Follow-up
	Enrollment /Baseline	12 Mo. Visit	24 Mo. Visit	36 Mo. Visit	
≥ 5 and <6 year	5 yr. lead data	6 yr. lead data	7 yr. lead data	8 yr. lead data	9 yr. lead data
≥ 6 year	6 yr. lead data	7 yr. lead data	8 yr. lead data	9 yr. lead data	

Patients eligible for extended follow-up are those already enrolled with QuickSite/QuickFlex leads that have not previously withdrawn and have a QuickSite/QuickFlex lead that will contribute to a second subgroup cohort with an additional year of follow-up.

In order to maintain an unbiased study design, all eligible patients will be approached to provide consent for extended follow-up. SJM will provide study sites with a list of all eligible patients upon approval of this protocol. After eligible patients have been approached to consent for extended follow-up, complete the Extended Follow-Up Consent CRF using the EDC system.

Eligible patients must provide consent for extended follow-up prior to completing the 42 and 48 month follow-up visits (See Section 14.0). Refer to Table 3 and Section 3.4.2 for the requirements for these additional follow-up visits.

